### Product Description and Dosage Form

**SAMPLE PRODUCT INFORMATION TABLE:**

Product Description:				
Product Description and Dosage Form	Potency	Primary Packaging	Appearance	Storage Conditions (per label)
Rivaroxaban pill	20 mg	30 per bottle	pills	15-25°C

**Administration and handling****Important Food Effect Information**

The 15 mg and 20 mg XARELTO tablets should be taken with food. In the nonvalvular atrial fibrillation efficacy study XARELTO was taken with the evening meal.

For those randomized to Xarelto from Warfarin:

From warfarin to XARELTO, discontinue warfarin and start XARELTO as soon as the International Normalized Ratio (INR) is below 3.0 to avoid periods of inadequate anticoagulation.

..  
**Dosing in Nonvalvular Atrial Fibrillation**

For patients with creatinine clearance (CrCl) >50 mL/min, the recommended dose of XARELTO is 20 mg taken orally once daily with the evening meal. For patients with CrCl 15 to 50 mL/min, the recommended dose is 15 mg once daily with the evening meal

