#### **4. INVESTIGATIONAL PLAN AND STUDY DESIGN**

We propose a randomized, open label trial, to compare Rivaroxaban 20 mg oral once daily with food to warfarin (target international normalized ratio, 2.0 to 3.0) in patients with non-valvular atrial fibrillation. The primary endpoint will be CAC progression and key secondary objectives will be progression of total plaque, and development of new vulnerable plaques. Patients will be educated to maintain a low cholesterol diet through education to patients as well as medication compliance.

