**Figure 2.**

Day	What you do
Day 1	
 
You will have routine blood tests done and check your kidney function if needed.
 
You will have a CT scan (without contrast), and a CT angiogram (with contrast) (If you are a female who is able to have children, you will have a urine pregnancy test done before these tests.)
 
For Group 1, continue taking warfarin.
 

	
 
• For Group 2, begin taking assigned study drug once a day for the next 12 months. Keep taking until the end of study, unless told to stop by the study doctor or his staff.
 

3 Months	
 
• For Group 2, get new supply of study drug
 
• For both groups, we will ask you about changes in your health and medications and about visits to the doctor, emergency room or other outpatient clinic (for example, urgent care center).
 

6 Months	
 
• For Group 2, get a new supply of study drug
 
• For both groups, we will take blood for routine blood tests.
 
• For both groups, we will ask you about changes in your health and medications and about visits to the doctor, emergency room or other outpatient clinic (for example, urgent care center).
 

9 Months	
 
• For Group 2, get new supply of study drug
 
• For both groups, we will ask you about changes in your health and medications and about visits to the doctor, emergency room or other outpatient clinic (for example, urgent care center).
 

12 Months	
 
• We will take blood for routine blood tests,
 
• You will undergo a CT scan (without contrast) and CT angiogram (CT scan with contrast). (If you are a female who is able to have children, you will have a urine pregnancy test done before these tests.)
 
• You are done – the study is complete.
 

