### **Key Exclusion Criteria:**

1. Atrial fibrillation due to a reversible cause, moderate or severe mitral stenosis, or conditions other than atrial fibrillation that require anticoagulation (e.g., a prosthetic heart valve)
2. Prior rivaroxaban use.
3. A need for aspirin at a dose of  $>165$  mg a day or for both aspirin and clopidogrel,
4. Renal insufficiency (serum creatinine level of 12.5 mg per deciliter or calculated creatinine clearance of  $<50$  mL per minute).
5. Serious bleeding event in the previous 6 months or a high risk of bleeding (eg, active peptic ulcer disease, a platelet count of  $<100,000/\text{mm}^3$  or hemoglobin level of  $<10$  g/dL, stroke within the previous 10 days, documented hemorrhagic tendencies, or blood dyscrasias)
6. Weight in excess of 325 pounds
7. Resting hypotension (systolic blood pressure of  $<90$  mmHg) or resting hypertension (systolic blood pressure of  $>170$  mmHg or diastolic blood pressure of  $>110$  mmHg).
8. History of active malignancy requiring concurrent chemotherapy.
9. Any unstable medical, psychiatric, or substance abuse disorder that in the opinion of the principal investigator is likely to affect the subject's ability to complete the study.
10. Known allergy to iodinated contrast material

11. Pregnancy or breast feeding

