## **6. TREATMENT**

Patients will be randomized to either stay on warfarin at current doses, managed by the warfarin clinic at Harbor-UCLA with target INR of 2-3 and come in for quarterly visits with INR checks and documented safety; or Rivaroxaban 20 mg once daily.

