**COMMON: Seen in 1% (1 in 100 people) to 10% (1 in 10 people)**

- Internal bleedings which may occur in stomach and intestines may result in a low blood count (anemia) or decrease in blood pressure (hypotension). Other common bleeding sites include eye bleeds, bleeding from gums, nose bleeds, dark urine, heavy menstrual bleedings, hematomas (collection of blood) on the skin and small bleeds under the skin, coughing up blood, bleedings from wounds and after surgical procedures.
- Abdominal and stomach pains
- Upset stomach
- Nausea
- Constipation
- Diarrhea
- Vomiting
- Fever
- Swelling (edema; swelling caused by a fluid build-up in the body)
- Decreased general strength and energy
- Bruises
- Some enzyme levels in blood may increase (such as liver enzymes called transaminases)
- Pain in limbs (arm or leg pain)
- Dizziness (feeling dizzy)
- Headache
- Kidney problems\*
- Itching
- Rash (skin rash)

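### The fixed 20 mg rivaroxaban assignment conflicts with the protocol's own renal dosing text for a patient at a creatinine clearance of exactly 50 mL/min at entry or one who falls to 50 or below on study

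*Combined protocol and SAP*

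**What the plan says.** **Fixed dose.** Section 4 (Investigational Plan and Study Design) proposes "to compare Rivaroxaban 20 mg oral once daily with food to warfarin", and the Study Design item repeats that dose. In Section 6 (Treatment), patients either stay on warfarin and "come in for quarterly visits with INR checks and documented safety; or Rivaroxaban 20 mg once daily". None of these places mentions renal function.

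**Dose by clearance.** Dosing in Nonvalvular Atrial Fibrillation (Section 7) gives 20 mg once daily above 50 mL/min, and then: "For patients with CrCl 15 to 50 mL/min, the recommended dose is 15 mg once daily with the evening meal". The food-effect text and the missed-dose text, also in Section 7, both refer to a 15 mg strength alongside the 20 mg one.

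**Supply.** The table headed "SAMPLE PRODUCT INFORMATION TABLE" has one row, a 20 mg pill.

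**Entry.** The Key Exclusion Criteria remove patients with "calculated creatinine clearance of $<50$ mL per minute". The upper age limit is 84.

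**Monitoring.** Bloods are scheduled at 0, 6 and 12 months (Laboratory Measurements). Serum creatinine and the Cockcroft-Gault formula are in Section 8.1. Figure 2 words the Day 1 check conditionally: "You will have routine blood tests done and check your kidney function if needed".

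**The concern.** The protocol gives two different statements of the rivaroxaban dose for the same patient and does not say which prevails. The renal exclusion looks as if it prevents this, but it applies once, at entry, and its cut-off does not meet the dosing bands cleanly. Treatment then runs for 12 months in patients who may be in their eighties.

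Two things are at stake. The first is safety conduct: an investigator holding a month-6 creatinine result that puts the patient in the 15 to 50 band finds one section pointing to one dose and another section to a different one. The second is interpretability. If the response is left to individual judgement, the treatment actually received in the rivaroxaban arm depends on decisions that nobody was asked to document. The bleeding analysis in Section 13 closes its window 2 days after the last dose, so a decision to stop drug on a creatinine result would also change which bleeding events are counted.

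**Working it through.** The plan states no figure to reproduce here. The check has three parts: compare the boundaries, find how far creatinine must move to cross the line, and look for a rule that resolves the conflict.

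**Step 1. Boundaries side by side.**

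| Clearance (mL/min) | Exclusion criteria | Sections 4 and 6 | Section 7 dosing text |
|---|---|---|---|
| 49.9 | excluded | not applicable | 15 to 50 band |
| 50.0 | eligible | 20 mg | 15 to 50 band |
| 50.1 | eligible | 20 mg | above-50 band |
| 60 | eligible | 20 mg | above-50 band |

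At entry the passages disagree at one value, 50. Above it they agree.

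**Step 2. Crossing on study.** The formula printed in Section 8.1 is

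CrCl = (140 − age) × weight × (0.85 if female) / (72 × creatinine).

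At fixed age and weight, clearance is inversely proportional to creatinine, so the rise that brings a baseline b down to 50 is b/50 − 1. The baselines are illustrative:

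- from 51: 51/50 − 1 = 2%
- from 55: 55/50 − 1 = 10%
- from 60: 60/50 − 1 = 20%
- from 70: 70/50 − 1 = 40%

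In individual terms (illustrative patients, creatinine in mg/dL):

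- Man, 80 years, 72 kg, creatinine 1.2: (60 × 72)/(72 × 1.2) = 50.0. He is eligible and sits on the boundary.
- Man, 78 years, 75 kg: (62 × 75)/(72 × 1.2) = 53.8; at creatinine 1.3, (62 × 75)/(72 × 1.3) = 49.7.
- Woman, 75 years, 65 kg: (65 × 65 × 0.85)/(72 × 0.95) = 52.5; at creatinine 1.0, (65 × 65 × 0.85)/(72 × 1.0) = 49.9.

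Ageing one year multiplies the estimate by (139 − age)/(140 − age). That is a fall of 1/70 = 1.4% at age 70 and 1/56 = 1.8% at age 84. Baselines up to 50 × 70/69 = 50.7 and 50 × 56/55 = 50.9 respectively reach 50 with no change in creatinine.

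**Step 3. Is there a governing rule?** Section 8.1 lists creatinine but attaches no dosing consequence to it. Figure 2 tells patients to keep taking the drug unless study staff tell them to stop, which is general discretion. The adverse-event text and the DSMB section cover recording and review. No section says whether Section 6 or the dosing text in Section 7 prevails once clearance is 50 or below.

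**A related ambiguity.** Section 8.1 computes a Cockcroft-Gault clearance but labels it eGFR in mL/min/1.73m², whereas the exclusion and the dosing bands are in mL/min. The value to hold against 50 is therefore not fully defined.

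**The case against.** The strongest reply is that the dosing section is worded as a recommendation, reads like product-label text, and can be taken as the specific renal rule beneath Section 6's general assignment. On that reading the sponsor has stated an instruction and only precedence and supply are unclear. This is a possible reading, but the protocol does not state it. A clinician could equally treat Section 6 as the trial's assigned treatment and Section 7 as background. Unstated precedence between two doses is the defect.

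Several stronger readings are tempting, and the documents do not support them:

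- *The product table gives every patient 20 mg.* It is headed as a sample, lists a strength and assigns no dose. It shows only that the other strength named in Section 7 is not listed.
- *On-study creatinine triggers nothing.* New or worsened laboratory abnormalities count as adverse events (Section 10), significant worsening on safety assessments must be recorded (Other Safety Considerations), Section 13 compares laboratory abnormalities by arm, and the DSMB receives reports every 6 months. What is missing is the link to the dose.
- *Baseline renal function may go unmeasured.* Figure 2 is patient-facing wording. The month-0 bloods, the creatinine in the panel and the clearance exclusion together already require the value. The conditional phrase is a minor inconsistency.
- *The risk section shows a renal hazard in this population.* The entry "Kidney problems" carries a footnote tying it to major orthopedic surgery of the lower limbs.
- *Lower clearance is shown to raise bleeding.* No section says so. Concern about bleeding is a reasonable inference, since major bleeding is the primary safety outcome, but it is not a finding from the documents.

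**Conclusion.** The contradiction is real and needs correcting, within limits. At entry it concerns one clearance value, 50 mL/min. Its practical weight lies with patients who enter above 50 and reach 50 or below during the 12 months, for whom a creatinine rise of 10% (from 55) or 20% (from 60) suffices at fixed age and weight.

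How many patients that is cannot be calculated. The documents give neither a clearance distribution nor a rate of decline, and even the enrolment figure is 110 in one place and 120 in another. Any count would be assumption alone.

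The point has no bearing on sample size or power, and no effect on the primary endpoint has been shown. It matters because it concerns the dose of an anticoagulant, is foreseeable in this age range, and costs little to resolve. The conclusion rests on reading the Section 7 dosing text as part of the protocol, since nothing marks it as inapplicable to the study. It implies nothing about which dose or clinical rule is right, or whether such a patient should have the month-12 contrast scan. Those are decisions for the sponsor and the investigator.

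**What to change.** The sponsor should:

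1. Reconcile Section 4, the Study Design item, Section 6 and the sample product table with the food-effect, dosing and missed-dose text in Section 7.
2. Align the exclusion cut-off with the dosing bands so that each clearance value, 50 included, falls under one rule, and state in Section 8.1 which quantity and unit is compared with 50.
3. State which text governs when an on-study clearance enters the 15 to 50 band.
4. Record on the CRF each patient to whom this happens and the action taken, and list them in the DSMB reports.
5. As a minor point, bring Figure 2's Day 1 wording into line with the exclusion criteria, the Laboratory Measurements schedule and Section 8.1.

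The cost is protocol wording and one CRF field, because creatinine is already in the safety panel. Depending on the rule the sponsor adopts, a further tablet strength may have to be supplied.

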**In case of Missed Dose**

If a dose of XARELTO is not taken at the scheduled time, administer the dose as soon as possible on the same day as follows:

- For patients receiving 20 mg or 15 mg once daily: The patient should take the missed XARELTO dose immediately.

At Study Conclusion (for those randomized to Xarelto):

*Switching from XARELTO to Warfarin* - No clinical trial data are available to guide converting patients from XARELTO to warfarin. XARELTO affects INR, so INR measurements made during coadministration with warfarin may not be useful for determining the appropriate dose of warfarin. Our approach will be to discontinue XARELTO and begin both a parenteral anticoagulant and warfarin at the time the next dose of XARELTO would have been taken

## 8. STUDY ASSESSMENTS AND PROCEDURES

### 8.1 Standard Safety Laboratory Panel

Hematology

- Hemoglobin
- Hematocrit
- Red blood cell count
- White blood cell count and differential
- Platelet count

Serum chemistry

- Aspartate Aminotransferase (AST, SGOT)
- Alanine Aminotransferase (ALT, SGPT)
- Alkaline Phosphatase (reflex to GGTP)
- Creatine Kinase (Creatine Phosphokinase) (CK) (CPK) (reflex to troponin)
- Total Bilirubin
- Uric Acid
- Blood Urea Nitrogen (BUN)
- Electrolytes - sodium, potassium, chloride, Total Protein, Albumin
- Serum Creatinine (Scr)

EGFR will be estimated by the method of **Cockcroft-Gault**:

Cockcroft-Gault CrCl =  $(140 - \text{age}) * (\text{Wt in kg}) * (0.85 \text{ if female}) / (72 * \text{Cr})$

The eGFR is expressed in mL/min/1.73m^2

- Females only: urine HCG pregnancy test (HCG minimum sensitivity of 25 IU/L). If a urine HCG test is positive, patient will be excluded

Data to be Collected: Routine demographic and cardiovascular clinical data have been collected for all patients in the study. For CAC, we will collect Agatston and Volume scores, number of lesions and density for each plaque. For CCTA-specific variables, we will quantify and characterize the following APCs by both manual and automated plaque characterization methods:

- Coronary artery plaque volume
- Non-calcified plaque volume
- Calcified plaque volume
- Plaque location
- Plaque length
- Plaque distribution
- Arterial remodeling
- Low attenuation plaque (Hounsfield unit density <30 HU)
- Spotty calcifications

*2b1a. Overview:* In a single session at baseline and followup, after phlebotomy and physical examination, each subject will receive sequential non-contrast followed by contrast scans. The entire scanning procedure will take approximately 30 minutes.

*Screening.* Subjects will be screened for contraindications for beta-blockers and nitroglycerin (PDE5 inhibitors). The desired heart rate for adequate image quality is  $\leq 70$  bpm. If the heart rate is above this level, a beta-blocker will be prescribed. If a beta blocker is contraindicated, a calcium channel blocker will be given instead.

*2b1b. Noncontrast scan:* This will be performed to measure CAC. Patients will be positioned within the scanner with ECG leads, and a rhythm strip will be viewed. After a scout film is obtained, standard calcium scoring imaging will be performed at the end of inspiration.

*2b1c. Contrast Scan.* One minute prior to the CT angiogram acquisition, sublingual nitroglycerin will be administered. Iodinated X-ray contrast will then be injected. When significant heart rate variability exists, retrospective imaging will be utilized. Breath hold acquisition will be performed over approximately 20 seconds. After the study, patients will be observed for at least 10 minutes.

*2b1d. Image reconstruction:* Cross-sectional cardiac CT images will be reconstructed using prospective ECG triggering from 65 to 85% by 5% increments, and transmitted to the reading site.

*2b1e. Reading Center:* The Reading Center for CTA will be based at our Academic-based Medical facility. The Center will coordinate and oversee the collection of the data, store backup copies of the data, read each scan, send the results to the DCC and maintain quality control.

#### *2b2. Coronary Artery Calcification (CAC)*

CAC will be calculated from the non-contrast images using standard methods and scores will be reported using the Agatston method as elsewhere described (33). A total CAC score will be determined by summing the individual lesion scores from each of 4 anatomic sites (left main, left anterior descending, circumflex, and right coronary). A volume score, independent of density, is also calculated using a standard algorithm. A single experienced reader, blinded to subject identity and randomization, will interpret all the scans using commercially available software.

#### *2b3. CT Angiography (CTA)*

*2b3a. Imaging Analysis.* The resulting thin CT sections will be transferred to a dedicated workstation for image analysis. Images will be post-processed in an independent workstation (GE Advanced Workstation®) by the reader independently, during a dynamic reading process. Curved maximum intensity projection (MIP) multiplanar reconstructions will be performed for each coronary artery segment at the end-diastolic frame or the frame with the least motion artifact. Based on the curved MIP, the reader will identify an area of abnormality and determine the point of minimum luminal diameter within the abnormal area. Multiplanar reformatting will also be used to generate cross-sectional images of coronary segments using semiautomated software (AW 4.6, GE Healthcare, Milwaukee WI). This yields a vessel centerline using the full-width-half-maximum standard method to delineate the contrast-filled vessel, as well as automatic maximum and minimum diameters at any cross-section along the vessel centerline. A cross-sectional 5mm MIP image will be reconstructed at this location and semi-automatic software will be used to outline the intimal surface providing cross-sectional vessel area. In cases where coronary segments are normal, the most proximal cross-sectional image will be used for analysis. CT values will be measured in the most visible images such as axial source or multiplanar images of the long axis at each site of the coronary arteries. For determining image quality, both qualitative and quantitative analysis will be performed. Each segment will be classified as poor, acceptable, good or excellent quality regarding the presence of motion artifact, which is defined as any discontinuation or blurring of the sharply defined vessel contour.

*2b3b. Plaque evaluation.* Plaque will be evaluated from both axial source images and multiplanar reconstruction images of the long axis at each site of the coronary arteries. CP will be defined as any structure with a density greater than the contrast-enhanced lumen that could be visualized separately from the lumen, which could be assigned to the coronary artery wall, and that could be identified in at least two independent planes. NCP will be defined as any discernible structure that could be clearly assignable to the vessel wall, which had a CT density less than the contrast-enhanced coronary lumen but greater than the surrounding connective tissue, and that could be identified in at least two independent planes (1). Each coronary segment (15 AHA standardized coronary segments) will be classified as either normal, containing NCP, containing MP with either predominantly NCP (<50% of plaque area occupied by calcium) or containing CP.

Reviewer will independently evaluate the contrast-enhanced scans by assessment of the axial slices of multiplanar reformations and of three thin-slab maximum intensity projections.

Percentage of coronary arterial stenosis will be estimated on a cross-sectional image obtained from reconstruction of standardized coronary segments. Stenosis will be evaluated in a scale of 0-4: 0 (normal segment without stenosis or plaque present), 1 (1% to 29% stenosis), 2 (30% to 49% stenosis), 3 (50-69% stenosis), and 4 ( $\geq 70\%$  stenosis). Segments with diameter  $<1.5$  mm will be graded as small and therefore unable to evaluate for stenosis. Segment Stenosis Score" (SSS) will be determined by summing the number of evaluable coronary segments with individual stenosis scores (maximum score = 60 (score of 4 for all 15 segments)).

*2b3c. Plaque Composition.* The presence of noncalcified atherosclerotic plaque tissue will be defined as any discernible structure in the coronary artery wall with a CT density less than the contrast enhanced coronary lumen but greater than the surrounding connective tissue.

Measurements will be obtained from manually traced regions of interests encompassing the noncalcified plaque proportions.

*2b3d. Plaque Quantification.* The calculation of the coronary plaque burden and volume will be performed on axial cross sectional images in a blinded fashion. The plaque area of each coronary plaque visualized in at least 2 adjacent slices (reconstructed slice thickness 0.6 mm) will be determined on all affected slices, and plaque volume will be assessed by multiplying the area by the slice thickness. Summing the total plaque per segment will be done, and compared with the subsequent scan in a blinded manner. Plaque burden will be reported in both a semi-quantitative and a quantitative (volumetric) manner; a plaque burden score will be developed to semi-quantitate the plaque in each participant. The AHA 15 segment model of the coronary arteries and visual semi-quantification of coronary artery calcific and non-calcific plaque will be used. Each plaque will be multiplied by 1 for small plaque volume, 2 for medium plaque volume and 3 for large plaque volume. "Plaque Burden Score" (PBS) will be determined by summing the number of evaluable coronary segments with individual plaque scores (maximum score = 45 (score of 3 for all 15 segments)). The "Percent Plaque Score" (%PS) will be calculated by (number of segments with plaque / total number of evaluable segments)  $\times 100$ . Both plaque burden score and percent plaque score will be evaluated as independent variables and compared to other measures in the study, as aforementioned. The protocol for quantitative plaque assessment (volume, in  $\text{mm}^3$ ) is fully described elsewhere (2). For each lesion identified, minimal lumen diameter and minimal lumen area will be determined as elsewhere described.

